Aim #2 : To assess the efficacy of the PP-MI intervention to increase moderate to vigorous physical activity (MVPA) at follow-up, compared to an MI-alone control condition, in patients who recently have experienced an ACS.

Hypothesis: The PP-MI intervention will be associated with greater improvements in MVPA compared to the control group at 12 (primary timepoint) and 24 weeks.

Aim # 3: To examine the efficacy of the PP-MI intervention on psychological health, health-related quality of life, and functional status.

Hypothesis: The PP-MI intervention will be associated with greater improvements in psychological health (optimism, positive affect, depression, anxiety), health-related quality of life, and functional status, compared to MI alone.

III. Participant selection

A. Inclusion/exclusion criteria

- Adult patients admitted to MGH or BWH inpatient units with a primary cardiac diagnosis of ACS (myocardial infarction [MI] or unstable angina [UA]) or who develop an ACS while in the hospital, OR adult patients admitted to a Partners institution who have experienced an ACS in the past 2 weeks and who have a Partners-affiliated primary care physician or cardiologist. To meet criteria for MI, eligible patients must meet at least two of three World Health Organization⁴⁸ criteria for an acute MI: typical chest pain, elevated cardiac enzymes, and electrocardiographic changes consistent with MI. For UA, participants must have new-onset angina within 2 months, exacerbation of previous angina with rest pain or with minimal exercise, or angina within 2 weeks of MI.
- Suboptimal adherence to health behaviors. This will be defined as a total item score of <15 (suboptimal) on three Medical Outcomes Study-Specific Adherence Scale (MOS SAS)^{49,50} items OR a total item score of 15 and a physical activity item score of ≤ 5 .

Exclusion criteria:

- Cognitive deficits, assessed via a 6-item cognitive screen⁵¹ used to assess appropriate participation of medically ill patients in research studies.⁵²⁻⁵⁴
- Medical conditions precluding interviews or likely to lead to death within 6 months, determined in consultation with the primary treatment team and cardiology co-investigator [name].

- Inability to perform moderate to vigorous physical activity, as defined by an inability to walk without aid of an assistive device such as a walker or cane, OR inability to walk at a steady pace for at least 5 minutes without stopping.
- Inability to communicate in English.

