- Inability to participate in physical activity.

Justification and description of inclusion/exclusion criteria

We are recruiting patients with a primary admission diagnosis of ACS, or patients who develop an ACS while in the hospital. ACS diagnosis will be clarified with the inpatient or outpatient care team and, as needed, adjudicated by cardiology co-investigator [name]. We are including patients with suboptimal adherence (as measured by the MOS SAS, which has been used in multiple prior studies assessing adherence in cardiac patients^{7,55}) to ensure that there is room for improvement in health behavior adherence. We chose a cutoff score of 15, which should allow inclusion of the vast majority of patients with an ACS to ensure an intervention that is applicable to most patients. We have used this scale and this cutoff in prior studies with good effect.

We are excluding patients with impaired cognition to ensure that participants are able to meaningfully participate in both the consent process and exercises, and are using the 6-item cognitive screen because this tool has been used in prior studies involving medically-ill patients. We are excluding patients with medical conditions precluding interviews or likely to lead to death within 6 months given that these patients may be unable to meaningfully complete study assessments or are at high risk of dying before study completion. We are excluding those who cannot complete physical activity, particularly MVPA, because this will not allow us to complete meaningful assessments of such activity with the accelerometer.

We chose to include only patients who speak English for the time being, given that essentially all PP interventions in the past (and our own experience) have utilized exercises in English, and this will allow us to hold more variables constant as we pilot test this work (i.e., if we included several languages and it was not effective, we would not know whether it was because the intervention was lacking or whether our language/cultural translations of the exercises were suboptimal). In the future, we plan to develop and include a manual in Spanish.

B. Source of participants and recruitment methods

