Participants will learn about relaxation response exercises and ways to incorporate these exercises into daily life.

Planning for the Future (Session 13)

Participants will review the information learned over the course of the program and think of ways to remain healthy after the end of the program.

Follow-up phone calls (Week 12 & Week 24). At Weeks 12 and 24, a member of the study staff will call participants to repeat most of the self-report questionnaires that were administered at baseline (Week 0). These questionnaires assess adherence to physical activity (a modified version of the IPAQ), adherence to medication (SRMA), and dietary adherence to a low-fat diet (MEDFICTS). Questionnaires will also assess optimism (LOT-R), state optimism (SOM), positive emotions (PANAS), overall health behavior adherence (MOS-SAS), anxiety/depression (HADS), stress (PSS-4), physical functioning (DASI), health-related quality of life (SF-12), and cardiac symptoms (WISE). Participants will also be asked about cardiac-related hospital readmissions and attendance at cardiac rehabilitation, to rate their overall satisfaction with the treatment they received for their cardiac condition (outside of this study) over the last 12 weeks on a scale of 1 (excellent) to 5 (poor), and some questions about ease of use of the study devices. In sum, these scales should take approximately 30-40 minutes to complete.

We will schedule all phone calls during times that are acceptable to participants to reduce intrusions in their lives. We will remind participants of their upcoming study sessions and follow-up phone calls by phone, letter, or e-mail depending on their preference. If participants would rather complete the follow-up questionnaires in written or e-mail form rather than over the phone, we will send them a paper or electronic packet at the time of the follow-up. Participants who choose to complete the follow-up questions through e-mail will be sent a PDF file that will contain no personal identifiable information including name, social security number, address etc. The PDF file will only be labeled with a secure study ID number, and all e-mail communications

will occur via firewalled Partners e-mail accounts (study members' accounts), rather than through outside e-mail servers to protect patient confidentiality.

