Baseline information about enrolled participants will also be obtained by study staff from participants, care providers, and the electronic medical record as required for characterization of our population. This information will include data regarding medical history (history of prior

acute coronary syndrome, coronary artery bypass graft, congestive heart failure, hypertension, diabetes mellitus, hyperlipidemia, and current smoking), current medical variables (admission diagnosis, renal function, and left ventricular ejection fraction), medications, length of hospital stay, alcohol use, cigarette use, and sociodemographic data (age, gender, race/ethnicity, living alone). This information will help us to ensure that the population we recruit is a representative population of patients suffering ACS. As with all data, this will be linked in our database only via a participant ID number, and we will only collect that information (above) needed to characterize our population.

Objective adherence data

We will measure physical activity using a multi-axial ActiGraph GT-3X+ accelerometer (Actigraph, Pensacola, FL) that provides second-by-second step counts. The ActiGraph is a square 1.5" device that can be worn over or under clothes at the waist, either on an elastic band around the waist or on a clip appended to the belt or waistband of pants. Activity data is downloaded through a USB port on the step counter. We will use these step counters to assess activity because they are often considered to be the standard for measuring habitual physical activity.^{77,78} We chose to use ActiGraph accelerometers because they are the most widely used monitors for research purposes and adequately discriminate between different levels of activity.^{79,80} We will measure activity (MVPA) during two independent seven day periods beginning during week 12 and week 24 respectively.

Psychological outcomes

At the baseline visit and 12- and 24-week follow-ups, we will use structured scales to obtain information about psychological outcomes and adherence to health behaviors:

- (a) Positive affect will be measured using the positive affect items on the PANAS, a well-validated scale used in other telephone-administered intervention trials.^{81,82}

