- (b) Baseline physical activity (prior to hospitalization) will be measured with a modified version of the IPAQ to capture an estimate of the number of minutes spent performing MVPA in the past week (or a typical week, if the past 7 days atypical). The IPAQ has been used and validated in medical cohorts.^{58,59}
- (c) Medication adherence will be measured using the SRMA, a two-item measure of the percentage of time patients report taking their heart medications in the past one and two weeks.
- (d) Dietary adherence to a low-fat diet will be measured with the MEDFICTS scale recommended by National Cholesterol Education Program (NCEP). It is a widely-used and well-validated measure of cholesterol and saturated fat-intake.

Exercise ratings

We will obtain self-report ratings from participants for each completed exercise on two domains (ease of completion, overall utility). Participants will be asked to rate the ease (“how easy was the exercise to complete) and utility (“how helpful was the exercise”) of each exercise on Likert scales of 0-10 (0 = “not easy” or “not helpful,” 10 = “very easy” or “very helpful”).

VI. Biostatistical analyses:

A and B. Specific data variables and study endpoints

Aim 1: (*feasibility, acceptability*; primary aim): To determine whether the PP-MI intervention is feasible and acceptable by participants.

Measures:

- Rates of intervention completion (recorded by study trainer)
- Follow-up completion of self-report and objective adherence measures
- Measures of ease and utility

The intervention will be considered feasible if (1) at least 70% of all exercises are completed, (2) self-report follow-up data is obtained in 85% of participants, and (3) full accelerometer data is obtained in 80% of participants. The intervention will be considered acceptable if participants rate the PP exercises as at least 6/10 on ease and at least 7/10 on utility.

Aim #2 (between-group differences physical activity): To assess which group (intervention or control) is associated with the greatest physical activity at 12 (primary timepoint) and 24 weeks post-enrollment, as measured by self-report International Physical Activity Questionnaire (IPAQ).

Measures:

- Physical activity (IPAQ) (primary health behavior outcome measure)

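### Aim 2 compares the arms on self-reported activity alone; accelerometer MVPA is collected at weeks 12 and 24 but is given no between-group analysis

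*Combined protocol and SAP*

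**What the plan says.** Section VI.A and B states that Aim 2 compares physical activity between the arms "at 12 (primary timepoint) and 24 weeks post-enrollment, as measured by self-report International Physical Activity Questionnaire (IPAQ"). Its measures list has one entry, "Physical activity (IPAQ) (primary health behavior outcome measure"). The Aim 3 list repeats IPAQ and has no accelerometer entry.

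The accelerometer is introduced in Section V.E under objective adherence data: "We will measure activity (MVPA) during two independent seven day periods beginning during week 12 and week 24 respectively". That section justifies it as a device widely regarded as the standard for habitual activity. Section III.A excludes patients who cannot do such activity "because this will not allow us to complete meaningful assessments of such activity with the accelerometer". In Section VI the device appears only under Aim 1, where feasibility requires that "full accelerometer data is obtained in 80% of participants".

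The Section II hypothesis is that PP-MI will be "associated with greater improvements in MVPA compared to the control group at 12 (primary timepoint) and 24 weeks"; it names no instrument. The Aim 2 model in Section VI.C also takes MVPA as its outcome and names IPAQ only for the baseline covariate.

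**The concern.** Section VI.D says the study will probably not be powered for a between-group test on the secondary outcome. The use it gives this comparison is to supply effect sizes for a larger, multisite trial. As planned, the activity effect size would come only from what participants say about themselves.

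Under Section IV.C participants are not blinded. The PP-MI sessions in Section V.A set an activity goal every week, whereas the control programme is described there as lacking specific activity goals. Participants coached weekly towards an activity target could report activity differently from those who are not, at the same true activity level. A self-report effect carried into a larger trial's sample size would carry any such difference with it. The device data that could be set beside it are already being collected.

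**Working it through.** The plan gives no power or sample-size figure for Aim 2, so there is none to reproduce. The check traces each instrument through the plan and then prices the remedy.

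**Where each instrument appears**

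| Place | IPAQ | ActiGraph |
|---|---|---|
| II, Aim 2 | not named (MVPA only) | not named (MVPA only) |
| III.A, justification of criteria | – | reason for an exclusion |
| V.A, Table 1, week 0 | yes | worn for familiarisation, not as a baseline |
| V.A and V.E, weeks 12 and 24 | yes | yes, seven days each |
| VI.A and B, Aim 1 | self-report completeness, 85% | completeness, 80% |
| VI.A and B, Aim 2 | only measure | absent |
| VI.A and B, Aim 3 | listed again | absent |
| VI.C, Aim 2 model | baseline covariate | absent |

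No between-group comparison of ActiGraph MVPA is stated anywhere.

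**Does MVPA identify the instrument?** Not by itself. Section V.E says the IPAQ is used "to capture an estimate of the number of minutes spent performing MVPA in the past week", and the follow-up calls repeat it: "These questionnaires assess adherence to physical activity (a modified version of the IPAQ"). Sections VI.A and B and VI.C therefore fit together as one IPAQ analysis.

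**Cost of adding the ActiGraph comparison**

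Inputs from the plan: 48 randomized (III.B), 85% self-report and 80% accelerometer completion (II and VI.A and B). Assumptions: 1:1 allocation (IV.C gives no ratio), completion exactly at those targets (which are minimums, not forecasts), and correlations with baseline IPAQ of 0.5 for follow-up IPAQ and 0.2 to 0.3 for ActiGraph MVPA. The plan gives no correlations.

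- IPAQ: 0.85 × 48 = 40.8, or 20.4 per arm.
- ActiGraph: 0.80 × 48 = 38.4, or 19.2 per arm.
- Difference: 1.2 per arm.

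Half-width of the 95% interval, in SD units, for one timepoint (a simplification of the mixed model): t(0.975, df) × √[(2/n)(1 − r²)], with df = 2n − 2, less 1 when the covariate is used.

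| Estimate | n per arm | r | Half-width (SD) |
|---|---|---|---|
| IPAQ, unadjusted | 20.4 | 0 | 0.633 |
| ActiGraph, unadjusted | 19.2 | 0 | 0.654 |
| IPAQ, adjusted | 20.4 | 0.5 | 0.549 |
| ActiGraph, adjusted | 19.2 | 0.3 | 0.625 |
| ActiGraph, adjusted | 19.2 | 0.2 | 0.642 |

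Adjusted ratios: 0.625/0.549 = 1.14 and 0.642/0.549 = 1.17. Unadjusted: 0.654/0.633 = 1.03. Most of the extra width comes from the weaker assumed cross-instrument correlation, not from the lost participants.

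**The case against.** The sponsor has a sound reason for IPAQ. Aim 2 concerns improvement, and the footnote to Table 1 in Section V.A says the week 0 device wear is not a baseline, so only IPAQ has a baseline on its own scale. Feasibility is also a proper use of accelerometer data in a pilot whose primary aim is feasibility. Both arguments stand as reasons to keep IPAQ. Neither is a reason to leave device data at weeks 12 and 24 without a comparison.

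The design also limits differential reporting. The follow-up assessor is blinded (IV.C). The control has parallel manuals, exercises and calls, includes activity sessions (Session 3 covers how to set goals), and both arms receive a pedometer (V.A). These safeguards count, but blinding the assessor does not blind the person answering.

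A reader might go further and infer that the Aim 2 instrument is open and could be chosen once results are known, because Sections II and VI.C name none and Section IX.C schedules outcome reviews. The documents do not support that. Section VI.A and B, the section that defines endpoints, names IPAQ in both the aim and its measures list, and that reasonably settles it. The review after four completers is directed at feasibility and acceptability. The one after 20 also monitors outcomes, but neither is described as an occasion to choose an endpoint. What remains in Sections II and VI.C is a mismatch of wording.

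**Conclusion.** The point holds in a limited form. Section VI settles Aim 2 on self-reported IPAQ and gives ActiGraph MVPA no between-group role, so the activity effect size meant for a larger trial would have no objective estimate beside it. That rests on the text alone.

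It does not follow that the IPAQ result is biased or that IPAQ is the wrong choice. Differential reporting is plausible given unblinded participants and the concentration of goal-setting in PP-MI, but the documents give no figure for it and none is claimed.

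The severity is modest. Aim 2 is secondary and the plan expects it to be underpowered. Both intervals would be wide: every half-width above exceeds 0.5 SD, an assumed reading of the plan's moderate effect. The two instruments side by side would show whether the activity signal depends on self-report, but could not settle a disagreement between them. The change is worth making because it is cheap and uses data already being collected.

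**What to change.** 1. In Section VI.A and B, Aim 2, keep IPAQ and add ActiGraph MVPA at week 12, with week 24 secondary, as an objective between-group outcome reported beside IPAQ.
2. Analyse it with the random-effects model already in Section VI.C, adjusted for baseline IPAQ. Describe the result as an adjusted difference at follow-up, not as a change, because the device has no baseline.
3. Name the outcome instruments in Sections II and VI.C so that they match Section VI.A and B, and state which one governs Aim 2. That choice is the sponsor's.
4. Fix a valid-wear rule in advance. The threshold in the remuneration paragraph of Section V.A (at least 5 days with at least 8 hours of wear) is one available option. It is now only a payment condition, and Section VI does not define full accelerometer data, so the number analysable under any rule may differ from the 80% target.

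The cost is a text amendment. There is no new data collection and the IPAQ analysis is unchanged. The downsides are one more reported outcome, a covariate measured on a different instrument and, under the assumptions above, about one fewer analysable participant per arm and an interval roughly 14% to 17% wider, for the added estimate only.

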Baseline Assessment and Initial visit (Week 0). The initial visit will occur at TCRC at MGH about two weeks after discharge from the hospital. Participants will first have their height and weight measured, then meet with a member of the study staff (the study “trainer”) and complete self-report questionnaires verbally or through a REDCap survey on an encrypted, secured iPad (participant preference). These questionnaires assess positive affect (Positive and Negative Affect Schedule; PANAS),⁵⁷ adherence to physical activity (a modified version of the International Physical Activity Questionnaire; IPAQ),^{58,59} adherence to medication (Self-Reported Medication Adherence; SRMA),⁶⁰ dietary adherence to a low-fat diet (MEDFICTS),⁶¹ cigarette use, and alcohol use (Alcohol Use Disorders Identification Test; AUDIT-C)⁶². Questionnaires will also assess general optimism (Life Orientation Test-Revised; LOT-R),^{63,64} and state optimism (State Optimism Measure; SOM), anxiety/depression (Hospital Anxiety and Depression Scale; HADS),⁶⁵ stress (Perceived Stress Scale-4; PSS-4),⁶⁶ physical functioning (Duke Activity Status Index; DASI)⁶⁷, health-related quality of life (Short Form-12; SF-12),⁶⁸ and cardiac symptoms (list from the Women and Ischemia Syndrome Evaluation study; WISE)⁶⁹. Participants also will report their race and ethnicity, as well as their marital status and whether or not they live alone. These scales should take approximately 30 minutes to complete.

After completing baseline questionnaires and receiving randomization, subjects in both groups will have an initial in-person session, in which the interventionist will provide a treatment manual specific to their condition, review the rationale for the initial exercise, and assign the exercise. If the patient is in the PP-MI condition, the trainer will explain the rationale for both the PP and MI (referred to as “goal setting”) portions of the program. The interventionist will also provide the participant with a copy of the MGH *Caring for Your Heart Handbook*, which all participants (regardless of condition) will receive. Participants in the MI-only control group will similarly have the rationale of the MI-based health behavior program explained to them, and will be assigned the first exercise. This will take 10-15 minutes.

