After explaining the program, the trainer will introduce to participants how to use a step counter (ActiGraph), and will ask the participant to wear an Actigraph GT3X+ accelerometer for 7 days to make sure they are comfortable using the device and that useable data can be obtained from the participant. ActiGraph accelerometers are validated as measures of physical activity and have been used in numerous studies of physical activity in patients with medical illness.⁷⁰ The accelerometer is a band with a small 1.5” square attached device that is worn around the lower waist, either on a waistband or clipped to the belt or waistband of clothing. It tracks the number

of steps taken. After explaining how to use the devices, the study trainer will schedule an appointment to call the participant in 1 week to review the first exercise over the phone. Lastly, participants in both conditions will also be given a digital pedometer (Omron) that clips on a belt or other article of clothing, to promote and track physical activity.

Table 1. Schedule of study events.

	Pre-enrollment	Week 0	Weeks 1-12	Week 12	Week 24
Cognitive screen	X				
Self-reported adherence (MOS-SAS)	X		X	X	X
Cigarette Use, Alcohol Use (AUDIT-C), Sociodemographic Data		X			
Chart review for baseline characteristics		X			
Self-report measures (DASI, SF-12, LOT-R, SOM, HADS, IPAQ, MEDFICTS, SRMA, PSS-4, PANAS, WISE)		X		X	X
Physical activity (step counter)		X*		X	X

*not used as a baseline measure, but as a way of getting the participant accustomed to the device

Weekly phone sessions (Weeks 1-12). After discharge from the hospital, participants will complete twelve 30-minute weekly phone sessions with a study trainer. The phone sessions primarily will include a review of the prior week's session content and a discussion of the rationale and assignment of the next week's exercise/assignment. These calls will be recorded so that a percentage of these recordings can be reviewed to ensure that both the intervention and control arms of the study are being delivered as described in the protocol and trainer manual.

Positive psychology plus motivational interviewing (PP-MI) condition (intervention)

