Aim #3 (psychological, health behavior, and functional outcomes): To examine the impact of the PP-MI intervention on self-reported adherence measures, psychological outcomes, functioning, and health-related quality of life at 12 (primary timepoint) and 24 weeks post-enrollment.

Measures:

- Self-reported adherence (MOS-SAS)
- Cigarette Use
- Physical activity (IPAQ)
- Medication adherence (SRMA)
- Dietary adherence (MEDFICTS)
- Alcohol Use (AUDIT-C)
- Psychological outcomes:
 - Positive emotions (PANAS)
 - Optimism (LOT-R)
 - State Optimism (SOM)
 - Depression/Anxiety (HADS-D and HADS-A)
 - Stress (PSS-4)
- Medical outcomes:
 - Physical functioning (DASI)
 - Health-related quality of life (SF-12)
 - Cardiac Symptoms (WISE)

C. Statistical methods

Data will be downloaded from REDCap into the Stata statistical package.

For Aim #1 (*feasibility, acceptability*), descriptive statistics will be used to report the proportion of exercises completed and proportion of participants who provided follow-up information.

Descriptive statistics also will be used to determine mean ratings of ease and utility for each exercise. Significance will be set at $p < .05$, using two-tailed statistical tests.

For the Aim #2 analyses (between-group differences in MVPA), we will perform random effects regression analyses with a random intercept for each participant. We will include group, time, and group x time interaction variables and will control for baseline physical activity (as measured by IPAQ). This will allow us to include participants with some missing data.

For the Aim # 3 analyses (between-group differences on psychological, health behavior, functional, and quality-of-life outcomes), we will use a random effects regression model with a random intercept for each participant, as in Aim #2.

D. Power analysis

The study will likely not be powered to definitely test for between-group differences on the secondary outcome, but it should be adequate to generate effect sizes for a larger, multisite efficacy trial by the end of the grant period. We hypothesize that the intervention will have a moderate effect size on physical activity (vs. the control condition), based on similar effect sizes for psychological interventions in cardiac patients.⁹⁵⁻⁹⁷

VII. Risks and discomforts

A. Complications of surgical/non-surgical procedures

No surgical or non-surgical procedures are being used in this study.

B. Drug side effects and toxicities

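### Cigarette use and AUDIT-C are listed as Aim 3 outcomes at Weeks 12 and 24 but are scheduled only at Week 0, so neither can be analysed as planned.

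*Combined protocol and SAP*

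**What the plan says.** Section VI.A and B sets Aim 3 as the effect of the intervention on self-reported adherence, psychological outcomes, "functioning, and health-related quality of life at 12 (primary timepoint) and 24 weeks post-enrollment". The measures listed under it include "Cigarette Use" and "Alcohol Use (AUDIT-C"). Section VI.C analyses the Aim 3 outcomes, health behaviors among them, with the same type of random-intercept regression as Aim 2, which has terms for arm, time and their interaction.

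The sections on data collection read differently:

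- **V.A, baseline visit.** The Week 0 questionnaires include "cigarette use, and alcohol use (Alcohol Use Disorders Identification Test; AUDIT-C").
- **Table 1.** The row "Cigarette Use, Alcohol Use (AUDIT-C), Sociodemographic Data" has one mark, at Week 0. A separate row, "Self-report measures (DASI, SF-12, LOT-R, SOM, HADS, IPAQ, MEDFICTS, SRMA, PSS-4, PANAS, WISE"), is marked at Weeks 0, 12 and 24 and contains neither item.
- **V.A, follow-up phone calls.** Staff will "repeat most of the self-report questionnaires that were administered at baseline (Week 0"), and the instruments are then named. Neither smoking nor alcohol appears.
- **V.E, baseline data.** Alcohol and cigarette use are listed among the variables that characterize the study population.
- **V.E, self-reported adherence outcomes.** Only MOS SAS, IPAQ, SRMA and MEDFICTS are given.

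**The concern.** An outcome at 12 and 24 weeks needs a measurement at 12 and 24 weeks. For these two measures the analysis section promises a between-arm comparison that the assessment schedule cannot supply. Staff who follow Table 1 and the call description would not ask the questions, and answers for a given timepoint cannot be collected once that call has passed.

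Two things are at stake if the items are meant as outcomes. Section VI.D says the trial should generate effect sizes for a larger study, and it would generate none for these two behaviors. The final report would also have to leave out two listed outcomes, which a reader could take for selective reporting when the real cause is a scheduling gap.

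**Working it through.** There is no planned figure to reproduce. The check compares the Aim 3 list with what is collected after baseline.

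**Step 1. Count the Aim 3 measures (Section VI.A and B).** MOS-SAS, cigarette use, IPAQ, SRMA, MEDFICTS, AUDIT-C, PANAS, LOT-R, SOM, HADS, PSS-4, DASI, SF-12 and WISE make 14 printed lines, or 15 if HADS-D and HADS-A are counted separately.

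**Step 2. Count what is scheduled at Weeks 12 and 24.** In Table 1, MOS-SAS (1) plus the repeated self-report row (DASI, SF-12, LOT-R, SOM, HADS, IPAQ, MEDFICTS, SRMA, PSS-4, PANAS, WISE = 11) gives 1 + 11 = 12. The follow-up call text names the same 12. Its extra questions cover readmissions, cardiac rehabilitation, satisfaction with care and ease of using the devices; none concerns smoking or alcohol.

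**Step 3. Subtract.** 14 − 12 = 2, and the two left over are cigarette use and AUDIT-C. As a share, 2/14 = 14%, or 2/15 = 13% with HADS split.

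| Source | Other 12 Aim 3 measures | Cigarette use, AUDIT-C |
|---|---|---|
| VI.A and B, Aim 3 | Outcome at 12 and 24 weeks | Outcome at 12 and 24 weeks |
| Table 1, Week 12 and Week 24 | Marked | Not marked |
| V.A, follow-up call | Named | Not named |
| V.E | Described as outcomes | Filed as baseline data |

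**Step 4. Look for another source.** Section V.E describes the MOS SAS as covering diet, exercise and medication, so it carries no smoking or alcohol information. The release in Section IV.B that lets staff contact treaters at 12 and 24 weeks refers to treatment and outcomes in general and is not described as a source of either measure.

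**Step 5. Consequence for the model.** Section IV.C assigns the condition after the baseline questionnaires, so the Week 0 value precedes randomization. With no later value, the Aim 3 model has no outcome observations at Week 12 or 24 for these measures. The random intercept allows for some missing visits; it cannot help where every follow-up visit is missing for everyone.

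**The case against.** The strongest reply is that the two items are stray entries in the Aim 3 list. Table 1, the follow-up call and both parts of Section V.E treat them as baseline descriptors, and only the list in Section VI treats them as outcomes. On that reading no intended data are lost. The follow-up text also says that most baseline questionnaires are repeated, which does not expressly exclude these two, and Section V.E says in general terms that adherence to health behaviors is assessed at all three timepoints.

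Importance can be questioned as well. The Aim 3 hypothesis in Section II names neither behavior, neither arm has a smoking session, and alcohol appears only within one control-arm diet session (Session 7). The documents give no smoking rate. If 10% to 30% is assumed, 48 participants include about 5 to 14 smokers (0.10 × 48 = 4.8; 0.30 × 48 = 14.4), so a between-arm estimate would be imprecise.

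Part of this stands. The sponsor's intent cannot be settled from the text, the loss of data matters only if the items are meant as outcomes, and every outcome named in the Aim 3 hypothesis does have scheduled follow-up. But general wording does not schedule a questionnaire when the table and the itemized call both omit it. A low-information outcome that stays on the list still has to be measured or removed. Damage to the table in PDF reading is not an explanation either: the row carries a single mark, which could not cover three visits, and Sections V.A and V.E agree with it independently.

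**Conclusion.** The contradiction is real. Two of 14 listed Aim 3 measures (14%; 13% on a count of 15) have no scheduled assessment at Week 12 or Week 24, so neither can be analysed as a 12- or 24-week outcome under the plan as written. The Week 0 values remain usable to describe the sample or as covariates.

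The finding assumes that staff follow Table 1 and the itemized call, and that no undescribed source supplies the data. It is confined to Aim 3; the feasibility aim and the physical activity aim do not depend on it. It should be corrected, because the correction is cheap and is useful only before the follow-up calls take place.

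**What to change.** Choose one status for the two items and make all sections agree.

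- **If they are outcomes:** add the cigarette-use question and AUDIT-C to the Week 12 and Week 24 columns of Table 1, to the list in the follow-up phone call text, and to the outcome measures in Section V.E. Also state how cigarette use is recorded, since no instrument is named for it, and check that the Aim 3 model suits that type of variable. The cost is a few questions in a call already planned at 30 to 40 minutes.
- **If they are baseline descriptors:** delete both lines from the Aim 3 measures and leave Table 1 and Section V.E as they are. The cost is a two-line deletion.

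The first option is preferable if calls are still to come, because it keeps the listed outcomes estimable. If some participants have already passed a call without being asked, the amendment should give the date from which collection starts, and the report should state how many participants have data.
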